4 STUDY DESIGN

4.1 Overall Design

This is an open-label study to evaluate the efficacy and safety of lenvatinib in combination with pembrolizumab in participants with advanced melanoma previously exposed to an anti-PD-1/L1 agent. All-comers with regards to PD-L1 and BRAF status are eligible for enrollment if they meet all of the inclusion and none of the exclusion criteria. Disease progression on an anti-PD-1/L1 mAb (alone or in combination) for the treatment of advanced melanoma must be documented within 12 weeks following the participant's last dose with an anti-PD-1/L1 mAb (RECIST 1.1) and confirmed by a second scan showing progression no less than 4 weeks after the first scan (in the absence of rapid clinical progression) (iRECIST). The proportion of participants who have received combination anti-CTLA-4+PD-1/L1 therapy will be capped at 25%.

Approximately 100 participants will be enrolled into the study. After a Screening Phase of up to 28 days, participants will be treated with the combination of lenvatinib and pembrolizumab for up to 35 administrations of pembrolizumab (approximately 2 years) or until disease progression, unacceptable toxicity, investigator decision or participant decision, withdrawal of consent, or death, whichever occurs first. After completion of approximately 2 years of combination treatment, participants may receive lenvatinib monotherapy until disease progression or unacceptable toxicity. Participants may interrupt or discontinue pembrolizumab due to toxicity and continue with lenvatinib. Similarly, participants may interrupt or discontinue lenvatinib due to toxicity and continue with pembrolizumab. Participants may also discontinue study intervention due to unacceptable AEs, withdrawal of consent, intercurrent illness that prevents further administration of treatment, investigator's decision to discontinue the participant, noncompliance with study intervention or procedure requirements or administrative reasons requiring cessation of treatment.

The primary endpoint of OR will be assessed by BICR per RECIST 1.1 criteria. The secondary endpoints are PFS, OS, and DOR. Safety and tolerability will be assessed by clinical review of all relevant parameters including AEs, laboratory tests, vital signs, and ECG measurements, as appropriate.

After the end of treatment, each participant will be followed for the occurrence of AEs and spontaneously reported pregnancy as described in Section 8.4.

Participants who discontinue for reasons other than radiographic disease progression will have posttreatment follow-up imaging for disease status until disease progression is documented radiographically per RECIST 1.1, initiating a nonstudy cancer treatment, withdrawing consent, or becoming lost to follow-up, whichever occurs first.

Participants will be permitted to continue study intervention beyond RECIST 1.1-defined disease progression if the treating investigator considers that the participant may experience clinical benefit with continued treatment as per iRECIST, and the participant is tolerating study intervention. Treatment beyond progressive disease per iRECIST may be permitted following Sponsor consultation and approval.

All participants will be followed for OS until death, withdrawal of consent, or the end of the study.

Specific procedures to be performed during the study, as well as their prescribed times and associated visit windows, are outlined in the SoA in Section 1.3. Details of each procedure are provided in Section 8.

4.2 Scientific Rationale for Study Design

If the safety profile is acceptable and this combination improves ORR, this study could support the regulatory approval of the combination of pembrolizumab and lenvatinib in participants with unresectable or advanced melanoma previously exposed to an anti-PD-1/L1 mAb.

4.2.1 Rationale for Endpoints

4.2.1.1 Efficacy Endpoints

This study will use OR, defined as a best overall response of CR or PR, as assessed by BICR per RECIST 1.1 criteria as the primary endpoint.

Progression-free survival (PSF), OS, and DOR are secondary endpoints.

Progression-free survival (PFS) is an acceptable measure of clinical benefit for a late-stage study that demonstrates superiority of a new antineoplastic therapy, especially if the magnitude of the effect is large and the therapy has an acceptable risk/benefit profile. The use of BICR and RECIST 1.1 to assess PFS is typically considered acceptable by regulatory authorities. Images will be read by a central imaging vendor blinded to treatment assignment to minimize bias in the response assessments. In addition, the final determination of radiologic progression will be based on the central assessment of progression, rather than a local site investigator/radiology assessment. Real time determination of radiologic progression as determined by central review will be communicated to the site. Overall survival (OS) has been recognized as the gold standard for the demonstration of superiority of a new antineoplastic therapy in randomized clinical studies. Duration of response as assessed by BICR per RECIST 1.1 will serve as an additional measure of efficacy and is a commonly accepted endpoint by both regulatory authorities and the oncology community.

iRECIST will also be used by the local site to make treatment decisions once PD has been documented per RECIST 1.1 and verified by BICR.

OS is defined as the time from the first day of study intervention to death due to any cause.

For participants who demonstrate CR or PR, DOR is defined as the time from first documented evidence of CR or PR until disease progression or death due to any cause, whichever occurs first.

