7 DISCONTINUATION OF STUDY INTERVENTION AND PARTICIPANT WITHDRAWAL

7.1 Discontinuation of Study Intervention

Discontinuation of study intervention does not represent withdrawal from the study.

As certain data on clinical events beyond study intervention discontinuation may be important to the study, they must be collected through the participant's last scheduled follow-up, even if the participant has discontinued study intervention. Therefore, all participants who discontinue study intervention prior to completion of the protocol-specified treatment period will still continue to participate in the study as specified in Section 1.3 and Section 8.10.3.

Participants may discontinue study intervention at any time for any reason or be discontinued from the study intervention at the discretion of the investigator should any untoward effect occur. In addition, a participant may be discontinued from study intervention by the investigator or the Sponsor if study intervention is inappropriate, the study plan is violated, or for administrative and/or other safety reasons. Specific details regarding procedures to be performed at study intervention discontinuation are provided in Section 8.1.9.

A participant must be discontinued from study intervention but continue to be monitored in the study for any of the following reasons:

- The participant or participant's legally acceptable representative requests to discontinue study intervention.
- The participant has a medical condition or personal circumstance, which, in the opinion of the investigator and/or Sponsor, placed the participant at unnecessary risk from continued administration of study intervention.
- The participant has a confirmed positive serum pregnancy test.
- Progressive disease as verified by investigator.

Note: Participants will be permitted to continue treatment beyond confirmed RECIST 1.1-defined progression if investigator-assessed clinical stability is observed, and the participant is tolerating study intervention (Section 8). Treatment beyond progressive disease per iRECIST may be permitted following Sponsor consultation and approval.

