Per iRECIST (Section 8.2.1.5), disease progression should be confirmed by the site 4 to 8 weeks after site-assessed first radiologic evidence of progressive disease in clinically stable participants. Participants who have unconfirmed disease progression may continue on study intervention at the discretion of the investigator until progression is confirmed by the site, provided they have met the conditions detailed in Section 8.2.1.5. Participants who receive confirmatory imaging do not need to undergo the next scheduled tumor imaging if it is less than 4 weeks later; tumor imaging may resume at the subsequent scheduled imaging time point, if clinically stable. Participants who have confirmed disease progression by iRECIST, as assessed by the site, will discontinue study intervention. Treatment beyond disease progression per iRECIST may be permitted upon Sponsor consultation and approval.

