8.2.1.4 RECIST 1.1

RECIST 1.1 will be used by BICR as the primary measure for assessment of tumor response, date of disease progression, and as a basis for all protocol guidelines related to disease status (eg, discontinuation of study intervention). Although RECIST 1.1 references a maximum of 5 target lesions in total and 2 per organ, this protocol allows a maximum of 10 target lesions in total and 5 per organ, if clinically relevant, to enable a broader sampling of tumor burden.

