8.2.1.5 RECIST 1.1 for Immune-based Therapeutics (iRECIST)

iRECIST is based on RECIST 1.1 but adapted to account for the unique tumor response seen with immunotherapeutic drugs. iRECIST will be used by the investigator to assess tumor response and progression and make treatment decisions. When clinically stable, participants should not be discontinued until progression is confirmed by the investigator, working with local radiology, according to the rules outlined in Appendix 8. This allowance to continue study intervention despite initial radiologic PD takes into account the observation that some participants can have a transient tumor flare in the first few months after the start of immunotherapy, and then experience subsequent disease response. These data will be captured in the clinical database.

Clinical stability is defined as the following:

- Absence of symptoms and signs (including worsening of laboratory values) indicating progression of disease
- Absence of rapid progression of disease or of progressive tumor at critical anatomical sites (eg, cord compression) requiring urgent alternative medical intervention
- No decline in ECOG performance status
- No requirements for intensified management, including increased analgesia, radiation, or other palliative care

Any participant deemed clinically unstable should be discontinued from study intervention at site-assessed first radiologic evidence of PD and is not required to have repeat tumor imaging for confirmation of PD by iRECIST.

If the investigator decides to continue treatment, the participant may continue to receive study intervention and the tumor assessment should be repeated 4 to 8 weeks later to confirm PD by iRECIST, per investigator assessment. Images should continue to be sent in to the CIV for retrospective BICR.

If repeat imaging does not confirm PD per iRECIST, as assessed by the investigator, and the participant continues to be clinically stable, study intervention may continue and follow the regular imaging schedule. If PD is confirmed, participants will be discontinued from study intervention.

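### The protocol names two readers, BICR and the investigator, for progression-based treatment decisions; and because scans may end at investigator PD, BICR PFS and DOR carry probably informative censoring that no sensitivity analysis tests

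*Combined protocol and SAP*

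**What the plan says.** On who calls progression and acts on it, one group of sections points to the central read:

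- Section 4.2.1.1 puts the central read above the site's: "the final determination of radiologic progression will be based on the central assessment of progression, rather than a local site investigator/radiology assessment". On timing, the same paragraph adds this commitment: "Real time determination of radiologic progression as determined by central review will be communicated to the site". A later paragraph has the site use iRECIST "to make treatment decisions once PD has been documented per RECIST 1.1 and verified by BICR".
- Section 8.2.1.4: RECIST 1.1 by BICR is the primary measure of response and progression, and also serves "as a basis for all protocol guidelines related to disease status (eg, discontinuation of study intervention".

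A second group points to the investigator:

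- Section 7.1 lists as a mandatory reason for stopping treatment: "Progressive disease as verified by investigator".
- Section 8.2.1.2: "Participants who have confirmed disease progression by iRECIST, as assessed by the site, will discontinue study intervention".
- Section 8.2.1.5: "iRECIST will be used by the investigator to assess tumor response and progression and make treatment decisions", and, where treatment goes on past first PD, "Images should continue to be sent in to the CIV for retrospective BICR". Table 7 and Appendix 8 follow the same scheme and contain no central verification step.

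On when scans end, Section 8.2.1.2 runs imaging to investigator-identified RECIST 1.1 PD unless treatment continues under iRECIST. Section 8.2.1.3 makes the discontinuation scan the last required one if iRECIST is not used. Section 1.3, footnote d, moves participants who stop with PD straight to survival follow-up.

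On the analysis, 9.6.1.2 (Table 9) and 9.6.1.4 (Table 10) count BICR PD or death. Without either, and also when the event comes after new anticancer therapy or after two or more consecutive missed assessments, the participant is censored at the relevant last assessment. Table 11 gives one censoring approach for each endpoint. Section 3 adds exploratory PFS and DOR by investigator iRECIST.

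**The concern.** There are two separate matters.

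First, a site reading 4.2.1.1 and 8.2.1.4 could reasonably wait for a central call before acting on progression. A site reading 7.1 or 8.2.1.5 would not. Sections 8.2.1.4 and 8.2.1.5 are adjacent, and sites could follow different procedures.

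Second, and whichever way the first is settled, the reader who can end scanning is not the reader who supplies the endpoint. If the investigator calls PD and BICR does not, scanning may stop and the participant leaves the BICR risk set as censored. Such participants are probably closer to a BICR progression than those who remain, so the Kaplan-Meier estimate is probably too high. Section 9.1 labels PFS and DOR key secondary endpoints, and Section 4.2 says the study could support approval. Their estimates will be read without a control arm.

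**Working it through.** **Readers compared.** No arithmetic applies here; two discordant cases show what the text requires.

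| Case | 4.2.1.1 / 8.2.1.4 | 7.1, 8.2.1.5, Appendix 8 | Also permitted |
|---|---|---|---|
| Investigator PD, clinically unstable, BICR stable disease | No BICR basis for stopping | Stop | Stopping on investigator decision (Sections 1.1, 4.1) |
| BICR PD, investigator stable disease | A basis for stopping | Continue | Treatment past RECIST 1.1 PD (Section 4.1; note in 7.1) |

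The named reader differs in both rows, but the last column leaves a permitted course in each.

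**Who is censored.** Clinically stable participants should have a repeat scan at 4 to 8 weeks, with images still going to BICR (8.2.1.5, Table 7). Scanning therefore ends at first investigator PD mainly in clinically unstable participants (Appendix 8) or where iRECIST is not used (8.2.1.3).

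**Size.** The plan states no figure to reproduce and no discordance rate, so the rates below are assumptions.

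- BICR PFS is exponential, with median 4.1 months (pembrolizumab, Section 2.2.1.4) or 7.6 months (the earlier melanoma cohort, Section 2.2.1.6). At 4.348 weeks per month these are 17.83 and 33.05 weeks. Both come from other populations and only set a range.
- Scans are every 9 weeks (8.2.1.2); PFS is read at Week 27.
- f = share with investigator PD one scan before BICR PD: 10%, 20% or 30%.
- u = share of these who stop scanning at that point; p = share of the stoppers who die within 18 weeks before new therapy, which counts as an event.
- The rest have a repeat scan at 6 weeks. If BICR PD is present by then, it is an event; if not, they are taken as iCPD and censored.

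True Week 27 PFS is 2^(−27/median): 2^(−27/17.83) = 35.0% and 2^(−27/33.05) = 56.8%.

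The extreme case (u = 1, p = 0) has a closed form. Let s = 2^(−9/median) and h = 1 − s. The hazard at the first scan is h. At the second and third it is h(1 − f)/(1 − fh), because discordant participants have left. The estimate is then s³/(1 − fh)². For the shorter median s = 0.705 and h = 0.295; with f = 0.3, 0.350/(1 − 0.0886)² = 42.1%. For the longer median s = 0.828 and h = 0.172; 0.568/(1 − 0.0516)² = 63.1%.

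The other cases were simulated with 1,000,000 participants per cell:

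| Scenario | Base 35.0%: f = 10 / 20 / 30% | Base 56.8%: f = 10 / 20 / 30% | Rise (points) |
|---|---|---|---|
| u = 0.25, p = 0.5 | 35.8 / 36.6 / 37.6 | 57.5 / 58.4 / 59.2 | 0.7 to 2.6 |
| u = 0.5, p = 0.25 | 36.2 / 37.5 / 38.7 | 57.9 / 59.0 / 60.3 | 1.1 to 3.7 |
| u = 1, p = 0 | 37.2 / 39.5 / 42.1 | 58.8 / 60.9 / 63.1 | 2.0 to 7.1 |

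Treating every repeat scan without BICR PD as iCPD is too severe, since Table 7 also allows iUPD, iSD, iPR and iCR with scanning continued. In the first row, if half of those scans are iCPD the rise is about 0.5 to 1.9 points; if none is, about 0.3 to 1.1.

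For comparison, the 95% half-width at n = 100 is 1.96·√(0.350·0.650/100) = 9.3 points and 1.96·√(0.568·0.432/100) = 9.7 points.

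A harsher model, with discordance possible from the first scan, 10% to 40% affected, and neither repeat scans nor separate deaths, gives about 1 to 14 points at Week 27. It ignores the repeat scan the protocol asks for, so it supports the direction but is not used for the size. DOR was not computed.

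**The case against.** The sections that sites operate from (7.1, 8.2.1.2, 8.2.1.5, Table 7, Appendix 8) consistently name the investigator, as does 4.2.1.1.2 within the rationale section. The analysis sections consistently use BICR. On this view the conflict is leftover wording in one rationale paragraph and one sentence of 8.2.1.4, which says a basis rather than the sole basis and may mean the criteria more than the reader. That is largely fair. It does not remove the conflict, because both 4.2.1.1 and 8.2.1.4 speak expressly of treatment and not only of endpoints.

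A reader might infer that the rules force opposite actions on the same participant. They do not: investigator discretion to stop and permission to treat past RECIST 1.1 PD are both written in. A reader might also infer that the endpoint definition is unsettled or that ORR is compromised. Section 9 keeps BICR as the endpoint source throughout, and ORR is not censored. A response left unconfirmed for this reason would need a first BICR response and investigator PD on the same final scan, so few are expected.

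On the censoring, every rate is assumed, the main range lies well inside sampling error, and repeat scans (including discretionary ones in unstable participants, Table 7) and qualifying deaths reduce the effect. All of that stands, and it limits the weight of the point. It does not answer it: sampling error is shown in the confidence interval and this bias is not. The exploratory iRECIST analyses use a different reader and different criteria, so they do not test the BICR censoring.

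**Conclusion.** The concern holds in a limited form. The protocol names two different readers for treatment decisions at progression; this is an inconsistency to correct, not a pair of incompatible orders. Separately, ending scans at investigator PD leaves probably informative censoring in BICR PFS, and probably in DOR, with an upward bias and no planned analysis to show its size.

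Under assumed discordance of 10% to 30%, Week 27 PFS is raised by roughly 0.3 to 4 points. It reaches about 7 only if every discordant participant stops scanning and none dies. The documents do not support a claim that the bias is large or that it could reverse a conclusion: there is no hypothesis test (9.3), and PFS and DOR are descriptive secondary endpoints in a single arm. Severity is minor to moderate. Confidence is high on the text conflict and on the missing sensitivity analysis, and low on the size.

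**What to change.** **Main change.** In 9.6.1.2 and 9.6.1.4, add a sensitivity analysis in which a participant whose scanning ended at investigator RECIST 1.1 PD without BICR PD counts as an event on the date of that investigator PD. Do not count PD that a repeat scan resolved to iSD, iPR or iCR. Report how many participants are affected. The primary ORR, PFS and DOR analyses stay as they are. This does not remove the censoring; it shows how far the estimates depend on it.

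**Wording.** The sponsor should state which reader it intends for treatment decisions. The text does not settle this: Table 7 still defines an unused abbreviation for verification of progression, and Appendix 8 keeps template text about PD not verified centrally.

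- If the investigator is intended, drop the real-time and BICR-verification wording from 4.2.1.1 and limit the central determination to the efficacy endpoints. Reword the first sentence of 8.2.1.4 so that BICR serves the efficacy endpoints and measurable disease at entry, and investigator RECIST 1.1/iRECIST governs treatment and discontinuation.
- If real-time central verification is intended, write that step into 7.1, 8.2.1.2, 8.2.1.5, Table 7 and Appendix 8. If scanning also had to continue until BICR verified PD, this route would reduce the censoring at source.

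**Cost.** With investigator-led decisions the cost is wording plus one extra analysis. Scans already go to the central vendor (8.2.1) and investigator assessments are captured in the database (8.2.1.5), so no further scans or visits are needed. Central verification would add operational work. The sensitivity analysis may give a less favourable PFS or DOR estimate.

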4.2.1.1.1 RECIST 1.1

RECIST 1.1 will be used by the BICR when assessing images for efficacy measures and when determining eligibility (Section 8.2.1.5). Although traditional RECIST 1.1 references a maximum of 5 target lesions in total and 2 per organ, this protocol has implemented a modification to RECIST 1.1 to allow a maximum of 10 target lesions in total and 5 per organ.

4.2.1.1.2 RECIST 1.1 for Immune-based Therapeutics (iRECIST)

RECIST 1.1 will be adapted to account for the unique tumor response characteristics seen following treatment with pembrolizumab (Section 8.2.1.5). Immunotherapeutic agents such as pembrolizumab may produce antitumor effects by potentiating endogenous cancer-specific immune responses. The response patterns seen with such an approach may extend beyond the typical time course of responses seen with cytotoxic agents, and patients treated with pembrolizumab may manifest a clinical response after an initial increase in tumor burden or even the appearance of new lesions. Thus, standard RECIST 1.1 may not fully capture the treatment benefits from immunotherapeutic agents such as pembrolizumab. Based on an analysis of participants with melanoma enrolled in KEYNOTE-001 (KN001), 7% of evaluable participants experienced delayed or early tumor pseudo-progression. Of note, participants who had progressive disease by RECIST 1.1 but not by the immune-related response criteria [Wolchok, J. D., et al 2009] had longer OS than participants with disease progression by both criteria [Hodi, F. S., et al 2014]. Additionally, the data suggest that RECIST 1.1 may underestimate the benefit of pembrolizumab in approximately 15% of participants. These findings support the need to apply a modification to RECIST 1.1 that takes into account the unique patterns of atypical responses in immunotherapy and enables treatment beyond initial radiographic progression, if the participant is clinically stable.

iRECIST assessment has been developed and published by the RECIST Working Group, with input from leading experts from industry and academia, along with participation from the US Food and Drug Administration and the European Medicines Agency [Seymour, L., et al 2017]. The unidimensional measurement of target lesions, qualitative assessment of nontarget lesions, and response categories are identical to RECIST 1.1, until progression is seen by RECIST 1.1. However, if a participant is clinically stable, additional imaging may be performed to confirm radiographic progression. iRECIST will be used by investigators to assess tumor response and progression and make treatment decisions as well as for exploratory efficacy analyses, where specified.

